7.4.2 ClinicalTrials.gov Requirements

The project is registered on ClinicalTrials.gov. (NCT03165981).

7.5 Human Subjects

In obtaining and documenting informed consent, the Investigator and study team will comply with the applicable regulatory requirements, Good Clinical Practices, and ethical principles. The parent or LAR must sign and date the written informed consent form prior to initiation of any study procedure.

1 INTRODUCTION

This document describes the statistical procedures that will be utilized for the CISA protocol Fever after Simultaneous versus Sequential Vaccination in Young Children. This statistical analysis plan (SAP) describes the methods of statistical analysis. The initial draft SAP (Version 0.1) was written prior to any data being analyzed in order to avoid bias. Any subsequent changes that occur to the study protocol warranting changes to the analysis procedures will be documented in the SAP. Table 1 below will be used for tracking changes to the SAP (both draft versions (0.X) and the final version (X.0)).

Table 1. Statistical Analysis Plan Versions

Version	Date of Approval	Major Changes from Prior Version
0.1	NA	NA
0.2	NA	Minor edits with the addition of linear regression analysis to address Secondary Objective b.2 average peak temperature. See addition to Section 8.2.
0.3	NA	Updates made to Secondary and Exploratory objectives based on CDC review. See Version 2.0 of the protocol from October 12, 2017.
0.4	NA	Minor edits and clarification based on call with CDC on December 13, 2017 and comments from an email on January 29, 2018.
1.0	February 6, 2018	Final SAP

2 PROTOCOL OBJECTIVES

2.1 Primary

- a) PO 1: To compare the proportions of children with fever following simultaneous versus sequential vaccination with PCV13, DTaP, and IIV during 2 visits. Children in the sequential vaccination group will receive PCV13 and DTaP at Visit 1 followed by IIV and health education at Visit 2. Children in the simultaneous vaccination group will receive PCV13, DTaP, and IIV at Visit 1, followed by a health education visit without vaccination at Visit 2. Fever will be assessed on the visit day of, and the day after (days 1-2) each visit.

2.2 Secondary

- a) SO 1: To compare the proportions of children with fever on day 1 and/or day 2 after Visit 1 and Visit 2 separately, in the simultaneous versus sequential vaccination group.
- b) SO 2: To compare the clinical importance of fever on day 1 and/or day 2 after Visit 1 and Visit 2 (separately and combined) in the simultaneous versus sequential group. Clinical importance is assessed based on severity of fever, duration of fever, and medical care utilization for fever.

2.3 Exploratory

- a) EO 1: To compare the height and duration of fever on day 1 and/or day 2 after Visit 1 and Visit 2 (separately and combined) in the simultaneous versus sequential group.
- b) EO 2: To compare the use of antipyretics for fever on day 1 and/or day 2 after Visit 1 and Visit 2 (separately and combined) in the simultaneous versus sequential group.
- c) EO 3: To describe and compare the level of severity of fever following Visit 1 and Visit 2 (separately) in the simultaneous versus sequential group.
- d) EO 4: To compare the proportions of children with fever 3-8 days after Visit 1 and Visit 2 (separately and combined) in the simultaneous versus sequential group.
- e) EO 5: To compare the clinical importance of fever occurring 3-8 days after Visit 1 and Visit 2 (separately and combined) in the simultaneous versus sequential group. Clinical importance is assessed based on severity of fever, duration of fever, and medical care utilization for fever.
- f) EO 6: To describe and compare the occurrence of solicited systemic adverse events on day 1-8 after Visit 1 and Visit 2 in the simultaneous versus sequential group.
- g) EO 7: To describe and compare the occurrence of febrile seizure and/or serious adverse events during the period of enrollment (i.e. from Visit 1 through 8 days after Visit 2) in the simultaneous versus sequential group.
- h) EO 8: To describe and compare the perceptions among parents/ legally authorized representatives (LARs) of the simultaneous versus sequential schedule experience.

3 STUDY ENDPOINTS

3.1 Primary

- a) POM 1.1: Proportion of children with fever (temperature $\geq 38.0^{\circ}\text{C}$ or $\geq 100.4^{\circ}\text{F}$) on day 1 and/or day 2 following Visit 1 and/or Visit 2.

3.2 Secondary

- a)
 - 1. SOM 1.1: Proportion of children with fever (temperature $\geq 38.0^{\circ}\text{C}$ or $\geq 100.4^{\circ}\text{F}$) on day 1 and/or day 2 following Visit 1.
 - 2. SOM 1.2: Proportion of children with fever (temperature $\geq 38.0^{\circ}\text{C}$ or $\geq 100.4^{\circ}\text{F}$) on day 1 and/or day 2 following Visit 2.
- b)
 - 1. SOM 2.1: Proportions of children with moderate/severe fever (GRADE 2 and/or 3) on day 1 and/or day 2 following Visit 1, Visit 2, and Visit 1 and Visit 2 combined.
 - 2. SOM 2.2: Average number of consecutive days of fever (temperature $\geq 38.0^{\circ}\text{C}$ or $\geq 100.4^{\circ}\text{F}$) per subject for fever starting on day 1 or 2 following Visit 1, Visit 2 and Visit 1 and Visit 2 combined. Note: fever starting on day 1 or 2 could continue through day 8.
 - 3. SOM 2.3: Proportion of children with medical care utilization (telephone call, medical office visit, emergency department visit, or hospital admission) for fever on day 1 and/or day 2 following Visit 1, Visit 2 and Visit 1 and Visit 2 combined.

3.3 Exploratory

a)

1. EOM 1.1: Average peak temperature of children with fever (temperature $\geq 38.0^{\circ}\text{C}$ or $\geq 100.4^{\circ}\text{F}$) on day 1 and/or day 2 following Visit 1, Visit 2, and Visit 1 and Visit 2 combined.
2. EOM 1.2: Total number of fever degree-days (temperature $\geq 38.0^{\circ}\text{C}$ or $\geq 100.4^{\circ}\text{F}$) on day 1 and/or day 2 per subject following Visit 1, Visit 2, and Visit 1 and Visit 2 combined.

b) EOM 2.1: Proportion of children with antipyretic use for fever on day 1 and/or day 2 following Visit 1, Visit 2 and Visit 1 and Visit 2 combined.

c)

1. EOM 3.1: Proportions of children with fever at different levels of severity (Grades 1, 2, and 3) on day 1 and/or day 2 following Visit 1 and Visit 2.
2. EOM 3.2: Proportions of children with fever at different levels of severity (Grades 1, 2, and 3) on days 3-8 following Visit 1 and Visit 2.
3. EOM 3.3: The proportion of children with fever at different levels of severity (Grades 1, 2,3 and all Grade) on days 1-8 following Visit 1 and Visit 2.

d)

1. EOM 4.1: Proportion of children with fever (temperature $\geq 38.0^{\circ}\text{C}$ or $\geq 100.4^{\circ}\text{F}$) on at least one day on day 3-8 following Visit 1.
2. EOM 4.2: Proportion of children with fever (temperature $\geq 38.0^{\circ}\text{C}$ or $\geq 100.4^{\circ}\text{F}$) on at least one day on day 3-8 following Visit 2.
3. EOM 4.3: Proportion of children with fever (temperature $\geq 38.0^{\circ}\text{C}$ or $\geq 100.4^{\circ}\text{F}$) on at least one day on day 3-8 following Visit 1 and Visit 2 combined.

e)

1. EOM 5.1: Proportions of children with moderate/severe fever (GRADE 2 and/or 3) on at least one day during days 3-8 following Visit 1, Visit 2, and Visit 1 and Visit 2 combined.
2. EOM 5.2: Average number of consecutive days of fever (temperature $\geq 38.0^{\circ}\text{C}$ or $\geq 100.4^{\circ}\text{F}$) per subject for fever starting on 3-8 days following Visit 1, Visit 2, and Visit 1 and Visit 2 combined. *Note: fever starting on day 3-8 could continue through day 8.*
3. EOM 5.3 Proportion of children with medical care utilization (telephone call, medical office visit, emergency department visit, or hospital admission) for fever on 3-8 days following Visit 1, Visit 2, and Visit 1 and Visit 2 combined).

f) EOM 6.1: The proportion of children with solicited systemic adverse events (excluding fever) at different levels of severity (Grades 1, 2, 3, and all Grades) on day 1-8 following Visit 1 and Visit 2.

g) EOM 7.1: The proportion of children with febrile seizure and/or serious adverse events during the period of enrollment (i.e. from Visit 1 through 8 days after Visit 2).

- h) EOM 8.1: Proportion of parents reporting positive and negative perceptions about their vaccination schedule experience will be determined for each survey item.

4 STUDY DESIGN

4.1 Study Description

This study is a prospective, randomized open-label clinical trial that will be conducted during the 2017-2018 influenza season. During the 2017-2018 season, approximately 280 children will be enrolled at Duke University Medical Center and Kaiser Permanente Northern California. Young children aged 12-16 months will be enrolled over a period of approximately 7 months. Children will be followed for up to 37 days following enrollment. Eligible children will be randomized to receive simultaneous or sequentially administered US-licensed PCV13, US-licensed DTaP vaccine, and US-licensed inactivated influenza vaccine (IIV). Children in the simultaneous group will receive PCV13, DTaP, and IIV vaccines at Visit 1, and then return for a health education visit without vaccination about 2 weeks later (Visit 2). Children in the sequential group will receive both PCV13 and DTaP without IIV at Visit 1, and then will receive IIV and health education about 2 weeks later (Visit 2). At Visit 1, children may also receive age- appropriate vaccines as recommended in the ACIP childhood immunization schedule. After Visit 1, non-study vaccines (U.S. licensed or investigational) are prohibited unless deemed a personal or public health priority by the health care provider caring for this patient or the study team.

Parents will record the occurrence of fever, solicited adverse events, medical care utilization, and receipt of antipyretics over 8 days following Visit 1 and Visit 2. In addition, febrile seizures and serious adverse events will be recorded for the entire study period (from enrollment through 8 days following the Visit 2) and will be assessed through parental report and chart review.

The first 10 children enrolled at Duke University Medical Center will be enrolled in a study pilot to quickly assess study feasibility benchmarks and make protocol adjustments if necessary. Data from pilot participants will also contribute to the analysis of primary, secondary and exploratory outcomes.

4.2 Sample Size and Power

Allowing for a 10% drop out rate given an initial N=280, there should be approximately 252 children enrolled into the study. If the true proportion of children who have fever on day 1 and/or day 2 after the first and/or second visit in the simultaneous group is 36% and the true proportion in the sequential group is 18%, then there is 90% power to reject the null hypothesis of no difference with N=126 per group with a two-sided alpha 0.05 level. This is based upon using a Mantel-Haenszel statistic in a stratified analysis to control for sites.

4.3 Randomization

Participants will be randomized (1:1) to receive either PCV13, DTaP and IIV simultaneously or sequentially (PCV13 and DTaP followed by IIV ~2 weeks later) using a permuted block randomization scheme stratified by study site (i.e., Duke University Medical Center and Kaiser Permanente Northern California). The first 10 children enrolled in the pilot at Duke University will be randomized in a block of 10 such that 5 children will receive simultaneous vaccination and 5 will receive sequential vaccination. The project statistician at Duke University will generate permuted block randomization schemes, which will be uploaded to REDCap. The randomization schedule will not be available to the study staff, so the next randomization

allocation will not be known before randomization occurs. Following confirmation of study eligibility criteria during Visit 1, participant randomization will be through REDCap with treatment allocation recorded on the CRF. This study will be open label and study staff and subjects will not be blinded to treatment arm assignments.

5 PARAMETERS OF ANALYSIS

5.1 Data Collection and Storage

Data will be handled according to the Duke Vaccine and Trials Unit SOP (DVTU M010). Data will be captured on paper CRFs and entered into the REDCap database. Diary data may be entered directly into REDCap, if the parent of the participant chooses to use this method.

5.2 Analytic Issues

There are two sites participating in the study and analysis of the primary objective will be stratified by site to account for this unit of randomization. Secondary data objectives may be stratified by site when applicable. There is one primary objective evaluated at the alpha 0.05 level and no adjustments to the alpha level will be made for secondary and exploratory analyses.

6 ANALYSIS POPULATIONS

6.1 Intent-to-Treat (ITT)

The ITT Population includes any participant that was enrolled, randomized into the study, and received at least one study vaccine at Visit 1.

6.2 Per Protocol

The Per Protocol Population is a subset of the ITT Population which excludes participants who do not provide valid temperature data on days 1 and 2 following Visit 1 and Visit 2 and/or participants with major protocol violations, as determined by the study investigators. The list of major protocol violations is located in **Appendix 1**.

Statistical analyses will be performed for both study populations, or the ITT Population only if no participants are excluded from the Per Protocol Population.

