8.2 Secondary Objectives

There are two secondary objectives for this study.

- a) The first secondary objective (SO 1) is to compare the proportions of children with fever on day 1 and/or day 2 after Visit 1 and Visit 2 separately, in the simultaneous versus sequential vaccination group. Fever on day 1 and/or day 2 after either visit will be counted as positive (1) for this analysis and no fever reported will be negative (0). Proportions at each visit will be compared between the simultaneous and the sequential vaccination groups using a Mantel-Haenszel statistic in a stratified analysis by site to control for the randomization blocks. The relative risk and corresponding 95% confidence interval for the occurrence of any fever on day 1 and/or day 2 after Visit 1 and Visit 2 separately will also be calculated. There are two separate statistical tests being performed at the alpha 0.05 level.
- b) The secondary objective (SO 2) is to compare the clinical importance of fever on day 1 and/or day 2 after Visit 1 and Visit 2 (separately and combined) in the simultaneous versus sequential group. Clinical importance is assessed based on severity of fever, duration of fever, and medical care utilization for fever. This information is captured on the memory aid form in the REDCap database.
 1. Severity of fever: To evaluate the severity of fever, we will present the proportions of children with the highest level of fever defined as Grade 2 and/or 3 ($\geq 38.6^{\circ}\text{C}$) on day 1 or day 2 following Visit 1, Visit 2 and Visit 1 and 2 combined by simultaneous and sequential vaccination groups.
 2. Duration of fever: To evaluate the duration of fever, the following analysis will be performed: The mean duration of any fever (in days) will be compared by simultaneous and sequential vaccination groups for children with fever that began on days 1 or 2 following Visit 1, Visit 2 and Visit 1 and 2 combined. Each consecutive day of fever on the memory aid will be counted per child per visit. Thus, a child could contribute a maximum of 8 days per study visit, should a fever be reported at each day on the memory aid. A child having fever on day 1, no fever on day 2, and fever on day 3 only has 1 day of fever.
 3. Medical care utilization for fever: We will present and compare the proportion of children with medical care utilization for fever (telephone contact, medical

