This document stands to serve as a general guideline for the study investigators to a priori define major protocol violations. Participants with major protocol violations will not be included in the Per Protocol Population.

Major Protocol Violations Defined:

1) Inclusion/Exclusion Criteria Violations

Did Not Meet Study Inclusion Criteria	At Study Entry Visit 1	During Period of Enrollment¹
1. 12 through 16 months of age (i.e. from the 1-year birthday until the day before 17 months of age) at the time of vaccination	X	X
2. Stable health as determined by investigator's clinical examination and assessment of child's medical history	X	
3. Has received all immunizations recommended by Advisory Committee for Immunization Practices (ACIP) during the first year of life with the exception of rotavirus and influenza vaccines.* *Immunizations recommended during the first year of life include: 3 doses of DTaP, 3 doses of PCV13, 2- 3 doses of inactivated polio virus vaccine, 3 doses of Hepatitis B vaccine, and 2 or 3 doses of Hib vaccine such that the primary Hib series is complete depending upon the brand used. (https://www.cdc.gov/vaccines/schedules/hcp/imz/child-adolescent.html).	X	X
4. The parent(s)/ legally authorized representative(s) LAR(s) intend for the child to receive DTaP and PCV13 in addition to this season's IIV	X	
5. The parent(s)/LAR(s) must be willing and capable of providing permission for their child to participate through the written informed consent process	X	
6. The parent(s)/LAR(s) must be able to comply with the requirements of the protocol (e.g., completion of the memory aid (either electronic or paper diary), return for follow-up visits, respects intervals between the visits and have telephone access.	X	
7. The parent(s)/LAR(s) must be English speaking	X	
8. The parent(s)/LAR(s) must agree to sign a medical release for the child so that study personnel may obtain medical information about the child's health (if needed)	X	
Met Exclusion Criteria		
1. History of any seizure (including febrile seizure) in the child or a febrile seizure in a first degree relative* *First degree relatives include biological parents or siblings	X	X
2. Has already completed influenza vaccination during the current season per ACIP recommendations* *Children needing two doses of influenza vaccine per ACIP recommendations and who are receiving a second dose of	X	X

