5. Received an experimental/investigational agent (vaccine, drug, biologic, device, blood product, or medication) after randomization or expects to receive an experimental/investigational agent during the remaining study period (up to 8 days after visit 2)	X	X
6. A moderate to severe acute illness within 24 hours of Visit 2* * This may result in a temporary delay of Visit 2 and/or vaccination. All vaccines can be administered to persons with a minor illness such as diarrhea, mild upper respiratory infection without fever.	X	X
7. A reported temperature greater than or equal to 100.4°F (38.0°C) within 24 hours prior to Visit 2 or a temperature (measured by temporal artery thermometer) greater than or equal to 100.4°F (38.0°C) at the time of Visit 2* *This may result in a temporary delay of Visit 2 and/or vaccination	X	X

8. Receipt of an antipyretic medication (acetaminophen or ibuprofen) within 24 hours prior to Visit 2* *This may result in a temporary delay of Visit 2 and/or vaccination	X	X
9. Parent(s)/LAR is planning to administer a prophylactic antipyretic or medication on the day of, and/or within 7 days following Visit 2* *This exclusion does not apply if the caretaker indicates he/she might administer antipyretics or analgesics after Visit 2 to reduce fever or pain	X	
10. Unable to receive an intramuscular injection in the thigh* * For example – a broken bone or cast for treatment of broken bone in a lower extremity, congenital anomaly in lower extremity precluding administration in the affected extremity or if deemed inappropriate by the study investigator	X	
11. Any condition deemed by the investigator to place the child at increased risk as a result of their participation in the study	X	

²If study team during the period of enrollment subsequent to Visit 2 becomes aware subject met exclusion meets the definition of a major violation

Procedural Violations

Visit 1

- Written informed consent not obtained
- Study eligibility not reviewed
- Temperature using the temporal artery thermometer not obtained
- Assigned study products administered prior to randomization
- Assigned study products not administered according to respective package insert specifications
- Study products received were not according to randomization assignment
- Study products not administered in thighs

Visit 2

- Visit 2 not done
- Study eligibility not reviewed
- Temperature using the temporal artery thermometer not obtained

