- Assigned study product (IIV if in sequential group) not administered according to package insert specifications
- Study products received were not according to randomization assignment
- Concomitant vaccine/s administered
- Study product not administered in thighs

Interval Between Visits 1 and 2

- The protocol notes that the maximal interval between Visit 1 (Day 1) and Visit 2 (Day 15 (+7)) is 21 days. If Visit 2 occurs between Day 15 and Day 25, it will not be considered a major Protocol Violation.

Parental assessments

- Parents did not measure temperature using temporal artery method

Other Major Protocol Violations

- Vaccines administered during any point during study period but not at Visit 1 or Visit 2
 - Emergency response
 - For other reason
- Use of immunosuppressive steroid dose (i.e. ≥ 14 days of daily receipt of 20 mg or 2 mg/kg body weight of prednisone or equivalent.) or other immune-modifying drugs or immunosuppressants from Visit 1 through 8 days after Visit 2

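### The single Per Protocol set requires a clean Visit 2, so Per Protocol analyses of Visit 1-only outcomes exclude children for events after the outcome was measured

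*Combined protocol and SAP*

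**What the plan says.** SAP 6.2 (and Protocol 6.2.1) defines one Per Protocol set. It is a subset of ITT that "excludes participants who do not provide valid temperature data on days 1 and 2 following Visit 1 and Visit 2" and drops children with major violations. Appendix 1 repeats the second rule: "Participants with major protocol violations will not be included in the Per Protocol Population".

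Appendix 1 then lists violations dated to Visit 2. They include:

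- "Visit 2 not done";
- meeting a Visit 2 exclusion criterion, for example "Receipt of an antipyretic medication (acetaminophen or ibuprofen) within 24 hours prior to Visit 2";
- no clinic temperature at Visit 2;
- another vaccine given at Visit 2;
- "Assigned study product (IIV if in sequential group) not administered according to package insert specifications".

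The set is not restricted to particular objectives: "Statistical analyses will be performed for both study populations, or the ITT Population only if no participants are excluded from the Per Protocol Population". SAP 8.2 tests fever by visit: "Proportions at each visit will be compared between the simultaneous and the sequential vaccination groups". Visit 1-only outcomes are SOM 1.1, the Visit 1 parts of SOM 2.1-2.3, the Visit 1 parts of EOM 1-3 and 5, and EOM 4.1.

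ITT (SAP 6.1) requires only enrolment, randomization and at least one study vaccine at Visit 1. Protocol 4.4 keeps the data collected before a vaccinated child withdraws.

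**The concern.** At Visit 1 the study vaccines differ between arms only by IIV, so SOM 1.1 is the most direct measure of what adding IIV to PCV13 and DTaP does to fever. Its outcome is complete on Day 2, and Visit 2 is on Day 15 or later. The Per Protocol version nevertheless requires the child to have attended Visit 2, met no exclusion there, and supplied Day 1-2 temperatures afterwards. That is selection on events after the outcome.

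The selection need not act equally on the arms. The trial is open label, and Visit 2 is an injection in one arm and health education in the other. IIV not given according to the package insert at Visit 2 can occur only in the sequential arm. The Visit 2 exclusion for having already completed the season's influenza vaccination, read literally, is met in the simultaneous arm by any child whose Visit 1 IIV completed the course.

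Two things are at stake: usable Visit 1 data are left out of the Per Protocol analysis, and a difference between the ITT and Per Protocol results could reflect who came back for Visit 2 rather than adherence at Visit 1.

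**Working it through.** **Inputs from the documents** (SAP 4.2): 280 children randomized 1:1, 10% dropout, 126 per arm, 36% v 18% fever, two-sided alpha 0.05, 90% power. The 36% and 18% are rates for fever after either visit. They are borrowed below as Visit 1 rates for illustration, because the documents give no Visit 1-only design rates.

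**The plan's figure.** z = [0.18 x sqrt(126) - 1.96 x sqrt(2 x 0.27 x 0.73)] / sqrt(0.36 x 0.64 + 0.18 x 0.82) = (2.020 - 1.231) / 0.615 = 1.285, so power is 90.1%. The stated 90% reproduces; the point is about selection, not a wrong figure.

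**Data lost.** 280 x 10% = 28, or 14 per arm. If all of that loss were for Visit 2 reasons (assumption), a Visit 1 set would hold up to 140 per arm rather than 126. At the borrowed rates, power would be 92.8% rather than 90.1%.

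**Possible bias.** With fever rate p and retention r, the Per Protocol rate in an arm is p r(fever) / [p r(fever) + (1 - p) r(no fever)]. All loss rates below are assumptions.

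| Scenario | Simultaneous | Sequential | RR (true) |
|---|---|---|---|
| A. 10% lost in each arm, unrelated to fever | 36.0% | 18.0% | 2.00 (2.00) |
| B. Sequential loses 30% of febrile, 7.5% of afebrile; simultaneous 10% of all | 36.0% | 14.2% | 2.53 (2.00) |
| C. Simultaneous loses 20% of febrile, 5% of afebrile; sequential 10% of all | 32.1% | 18.0% | 1.79 (2.00) |

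- B, sequential: 0.18 x 0.70 / (0.18 x 0.70 + 0.82 x 0.925) = 0.126 / 0.8845 = 14.2%. Overall loss in that arm is 11.6%.
- C, simultaneous: 0.36 x 0.80 / (0.36 x 0.80 + 0.64 x 0.95) = 0.288 / 0.896 = 32.1%. Overall loss in that arm is 10.4%.

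Under a true null of 18% in both arms, the losses in B give RR 1.26 and a simulated rejection rate of about 12.5% instead of 5%; those in C give RR 0.87 and about 8%.

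**Outer bounds.** Of 140 per arm, 50.4 and 25.2 are febrile. Removing 14 per arm in the most extreme ways gives:

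- upper: (50.4/126) / (11.2/126) = 4.50, difference 31.1 points;
- lower: (36.4/126) / (25.2/126) = 1.44, difference 8.9 points.

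These show only what a 10% loss leaves open.

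**Scale against sampling error.** For RR 2.00 with 126 per arm, SE(log RR) = sqrt(1/45.36 - 1/126 + 1/22.68 - 1/126) = 0.224, so the 95% interval is about 1.29 to 3.10. B and C both lie inside it. B turns on about five children: 25.2 x 0.30 = 7.6 febrile children lost, against 2.5 at 10%.

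**The case against.** The strongest reply is that the unconditioned analysis is already planned. Every Visit 1 outcome is also analysed in ITT, which ignores Visit 2, and these are secondary or exploratory outcomes without alpha adjustment. This stands, and it confines the point to the Per Protocol results.

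Second, nothing in the documents shows that Visit 2 loss depends on Visit 1 fever. Visit 2 is at least 13 days after Visit 1 vaccination is assessed for Day 2 fever, the Visit 2 fever, illness and antipyretic criteria look back only 24 hours and may simply delay the visit, Appendix 1 tolerates a Visit 2 up to Day 25, and parents must intend IIV and be able to return. This also stands: dependence may be weak.

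Third, the intervention is a two-visit schedule, so one set of children who completed it gives a common denominator, and the SAP 7.2 flow chart will show missed visits and both populations by arm. That is a fair reason to keep the two-visit set for combined outcomes. It does not justify it for Visit 1-only outcomes, and the flow chart does not break exclusions down by Visit 1 fever.

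Finally, the temperature rule could be read as excluding only children without data after both visits. Even so, the missed-visit violation in Appendix 1 removes a child with complete Visit 1 data.

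**Conclusion.** The point holds for the Per Protocol analyses of Visit 1-only outcomes. The documents establish that these analyses condition on later events, some of them arm-specific. The loss of Visit 1 data is up to about 14 per arm if all of the planned 10% loss is for Visit 2 reasons; that 10% is a dropout allowance, not a forecast of Per Protocol exclusions.

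A reader might infer that the trial's Visit 1 comparison is biased, or that its relative risk will be inflated. The documents do not support that. ITT answers the same question without the conditioning, the primary composite properly needs both visits, and the size and direction of any Per Protocol bias rest wholly on assumed loss rates. If loss is unrelated to Visit 1 fever, there is no bias, only fewer children. This is a worthwhile, inexpensive correction and not a threat to the main result.

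**What to change.** Define Per Protocol by outcome window in SAP 6.2 and Appendix 1:

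- **Visit 1-only outcomes:** valid temperatures for the window analysed (Days 1-2, or Days 3-8 or 1-8 where the outcome uses them), and no major violation occurring up to the end of that Visit 1 window.
- **POM 1.1 and combined outcomes:** keep the both-visit rule.
- **Visit 2-only outcomes:** valid data for the Visit 2 window and no violation up to its end, with a note that this set still selects on attending Visit 2.

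State that Visit 1 inference rests first on ITT. Tabulate Per Protocol exclusions by arm, reason and Visit 1 fever status. Clarify whether the Visit 2 criterion on completed influenza vaccination counts study IIV given at Visit 1, since the literal reading acts on one arm.

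The cost is SAP wording, up to three population flags, and denominators that differ between Visit 1, Visit 2 and combined results. All of it uses data already collected.
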